### 3.5 Synthesising analysis, writing up and preparation of toolkit

Following the completion of the fieldwork, the qualitative and quantitative data from Phase 2 will be brought together by the whole research team to create an overarching understanding of what changes were made and how in each site; what facilitated or hindered the process; how different types of data were received and acted on; what impact (if any) the process had on measured patient experiences; and what we can learn about successful strategies and pitfalls to include in guidance for the NHS. Early explanations will be tested and refined at the final learning community meeting with staff and patient and family advisers. We have scheduled a writing workshop for the research team in month 22 and again in month 25; this is an approach we have used successfully in the past to share out writing tasks and produce and share initial drafts, which will then be refined further in between workshops. From these workshops we will produce both the final NIHR report and the NHS toolkit (see dissemination). We have allowed six months for this process; although analysis will have been ongoing since the start of fieldwork, it is our experience that successful analysis requires repeated revisiting and reflection on the data to develop a nuanced account.

#### 4 STUDY SETTING

The research will take place in six medical wards in NHS acute Trusts in England. Sites will be accessed initially through senior Trust management. As part of a national survey of Trust senior patient experience leads currently being conducted (with separate REC and HRA approvals), Trusts are being invited to express interest in becoming a case study site. Six Trusts will be selected and invited to nominate a medical ward team to take part.

Understanding how frontline staff use patient experience data for service improvement - an exploratory case study evaluation.

Protocol V1 09.02.16 HRA 180418

#### 5 SAMPLE AND RECRUITMENT

Because the study involves several components we describe the sampling and recruitment approach for each separately.

### 5.1 Eligibility criteria

#### 5.1.1 Inclusion criteria

Case study sites: Frontline medical wards in NHS acute hospital Trusts in England.

Baseline and follow up survey of patient experience: All patients discharged from the medical ward within a 3-month period with capacity to consent, or a family member responding on their behalf.

Baseline and follow-up interviews about patient experience: Patients or family members responding to the survey who also express interest in taking part in an interview as well.

Ethnographic case studies: staff members, patients or family members who get involved in quality improvement on one of the six wards; other staff members who work on the ward; members of the senior management team in the six Trusts: members of the research team.

#### 5.1.2 Exclusion criteria

Case study sites: Surgical or other non-medical wards in NHS acute hospital Trusts in England; community and mental health Trusts; Trusts in Scotland, Wales or Northern Ireland.

Baseline and follow up survey of patient experience: Patients discharged from the medical ward outside the relevant 3-month period; those without capacity to consent.

Baseline and follow-up interviews about patient experience: Those without capacity to consent; those unable to take part in an interview in the English language.

Ethnographic case studies: staff and patients from other wards; patients currently receiving care on the ward. (Ethnographic observations will be confined to quality improvement activities and are not designed to observe care being provided).

#### 5.2 Sampling, recruitment and consent

#### Case study sites

Size of sample: 6

Sampling technique: The sample will be purposive. The sampling frame will be informed by a combination of reanalysis of existing survey data and a new survey of NHS Trust patient experience leads currently being conducted. (This phase of the work is the subject of separate REC and HRA approval already obtained.) We are

Understanding how frontline staff use patient experience data for service improvement - an exploratory case study evaluation.

Protocol V1 09.02.16 HRA 180418

combining evidence from these different sources to investigate how Trusts a) perform on these measures and b) organise themselves to work on patient experience and respond to patient experience data. The aim is to gather summary-level data from these sources into a matrix to identify high, average and poor performing Trusts – in other words to see which Trusts consistently demonstrate high performance and strong engagement with patient experience, those which do not, and those where no clear pattern emerges.

Recruitment/sample identification: Using this matrix we will select 3 high performing Trusts and 3 with more mixed performance. Trusts are being invited to express interest in becoming involved when their patient experience lead completes the national survey mentioned above. We will approach potential case studies matching our sampling categories sequentially until we have agreed participation. In each site, a frontline medical ward team will then be identified to join the study.

Consent: Consent to case study participation will be expressed through formal agreement by the Chief Executive or designated officer, and research governance agreement in each Trust. Individual consent will also be sought from staff members, patients and family members involved (see below).

#### Baseline and follow up survey of patient experience

Size of sample: 240 per ward at baseline, and a further 240 per ward at post-intervention follow-up. Total 2880 across six wards. Expected response rate of 50%.

Response rate data from the NHS Friends and Family Test suggests that on average in acute Trusts approximately 80 people are discharged per ward every month. Using this as a guide, we anticipate an estimated sample size of 240 patients per ward. The average sample of 240 patients per ward should provide 120 responses, assuming a 50% response rate (the response rate for the NHS Inpatient Survey 2013 which uses a similar methodology was 49%). This will allow for a minimum detectable difference of 11 percentage points for wards in the pre and post surveys; a good compromise between sample power and avoiding an excessively long sampling period. This minimum detectable difference of 11 percentage points is calculated based on the number of responses we believe to be achievable from the survey based on typical ward-level activity. Achieving a larger sample and a greater sample power would involve increasing the numbers of patients going through the medical wards in the three month sampling period, and this is out of the research team's control. As such, we will not have access to the kinds of sample sizes required for high precision estimates and detection of small changes. Due to this, the pre-and post-intervention surveys should be viewed as one part of the overall package of information collected rather than the only source of evidence.

Sampling technique: Census of every patient discharged from the ward over a 3-month period at baseline and again at follow-up.

Recruitment/sample identification: The survey will be administered using a postal methodology. Trusts involved in case studies will be asked to undertake the mailout using their patient discharge records, thus avoiding any need for the research team to access personal data. It will be explained that the survey may be completed by the patient or by a family member representative if the patient lacks capacity to complete the survey. Replies will be mailed to the Picker Institute for analysis. Fieldwork will last for 12 weeks with 2 reminder mailings being sent to non-responders during this period. Before each mailing sites will be asked to carry out a DBS (Demographics Batch Service) check to check for any deaths. An opt-out approach will be used with all survey materials stating that participation in the survey is completely voluntary. Materials will provide clear instructions on how people can opt out if they wish. Survey respondents who are interested in taking part in an interview will be invited to

Understanding how frontline staff use patient experience data for service improvement - an exploratory case study evaluation.

Protocol V1 09.02.16 HRA 180418

register their interest on the survey. In this case, the research team will send the unique survey ID codes of those selected for interview to the Trust and ask for a list of names and addresses to be supplied.

The methodology (such as the use of reminders and the length of fieldwork) are based on best practice in social research. A sufficiently long fieldwork period and the use of reminders is particularly important for patient experience surveys covering acute care settings as this has been shown to improve the representativeness of results and obtain more feedback from people with poorer experiences.

Consent: Completing and returning the survey will be taken as consent to participate. It will be explained to all participants that if they tick the box registering interest in being interviewed, they will be agreeing for the hospital to pass on their name and address so that the research team can send them more information, but that all answers they provide on the survey will remain entirely anonymous and will not be individually identifiable.

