Whilst the NHS Inpatient Survey shows small incremental improvements in some aspects of experience, including information provision, communication with staff, hospital cleanliness, and privacy (12), the pace of change remains slow on some of the most important questions for person-centred care (12-13). Only 54% of patients feel 'definitely' as involved as they want to be in decisions about their care, and only 50% feel doctors and nurses 'definitely' gave their families all the information they needed (12). Furthermore, 79% of patients said they had not been asked during their stay in hospital to comment on the quality of their care. Although this was an improvement on the 86% saying they had not been asked in 2012, it nonetheless indicates a substantial missed opportunity to learn from patients.

[name] Board research into how Trust boards use patient experience data found substantial variation in what data were collected but more importantly in the degree to which they were effectively analysed and used to improve services (14). Strikingly, the research found that over 95% of the time, hospital boards' minuted response to patient experience reports was to note the report but take no further action. Examples where patient experience data was used to spark debate and action were rare, as were examples of non-executive directors challenging performance on patient experience measures. Understanding how to use qualitative evidence, including narrative and observational data, as well as numerical evidence can be

Understanding how frontline staff use patient experience data for service improvement - an exploratory case study evaluation.

Protocol V1 09.02.16 HRA 180418

challenging (14-16), and this is undoubtedly one of the key areas where Trusts need support and training. Meanwhile, they also face an explosion of online sources of patient experience data and social media (e.g. NHS Choices, Care Connect, Patient Opinion and Twitter) with little guidance on how to use them.

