### 3.4 Post-intervention survey

The local baseline patient survey will be repeated a year on with a new set of patients to measure what, if any, change has occurred in measured patient experience following local quality improvement work. This will again be a postal survey with the same anticipated sample size of 240 per ward and will be sent to a census of all discharged patients from the six participating wards.

Results will be compared to data from the pre-intervention survey to see if there are any detectable ward-level changes to question scores. To explore whether ward level changes are observable at a Trust level, results (for those questions that map) will also be compared to Trust level data from the most recent NHS Adult Inpatient Survey.

The main outcome measure (or measures if all wards cannot be evaluated on the same measure) used for evaluating change will be determined through discussions amongst the research team, the project steering

Understanding how frontline staff use patient experience data for service improvement - an exploratory case study evaluation.

Protocol V1 09.02.16 HRA 180418

group, and with input from each ward team. This approach has the added benefit of allowing participating Trusts to be involved in the selection of measures, increasing their sense of ownership and 'buy-in' to the study.

Forty-eight in-depth interviews with patients and family or carers will also be carried out to gather more detailed information on the quality of the experience of recently discharged patients.

Reports showing survey and interview data for each case study site will be generated. They will detail:

- Response rate information
- The demographic profile of respondents
- Results for each question in the survey (with historical and Trust-level comparisons where appropriate). Caveats about interpretation of the data and the limits of significance testing will also be noted.
- Free text comments included as part of the survey
- Results from the in-depth interviews

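### The 11-point minimum detectable difference per ward is stated without power, alpha or baseline, and at 80% power it holds only for rises from about 84% or more

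*Protocol*

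**What the plan says.** The survey part of Protocol section 5.2 sets the sample at "240 per ward at baseline, and a further 240 per ward at post-intervention follow-up". It then says: "The average sample of 240 patients per ward should provide 120 responses, assuming a 50% response rate". As support it cites the 49% response to the 2013 NHS Inpatient Survey. The conclusion drawn is: "This will allow for a minimum detectable difference of 11 percentage points for wards in the pre and post surveys". This is described as "a good compromise between sample power and avoiding an excessively long sampling period", and a later sentence says that the figure "is calculated based on the number of responses we believe to be achievable from the survey based on typical ward-level activity".

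No power, significance level, sidedness, test or baseline proportion is given. Section 3.4 settles the structure of the comparison: "The local baseline patient survey will be repeated a year on with a new set of patients". The two waves are therefore separate groups of patients. The same section leaves the main outcome measure, which may differ between wards, to be agreed later.

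Section 5.2 also says that the sample cannot support high precision or the detection of small changes, and that the surveys are one part of the evidence. Sections 3.1 and 3.4 promise cautions about interpretation and significance testing in every site report.

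**The concern.** A minimum detectable difference means something only with a stated power, significance level and baseline. With 120 against 120, the usual convention (two-sided 5%, 80% power) gives a figure well above 11 points for questions in the middle of the scale. Such questions are plausible targets. Section 1 illustrates slow national progress on person-centred care with "Only 54% of patients feel 'definitely' as involved as they want to be in decisions about their care" and with a 50% result on information given to families. Section 3.1 says that the inpatient questions will include involvement in decisions.

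The figure is the protocol's only numerical guide to what a ward comparison can show. Section 3.4 uses the comparison to look for ward-level change, and section 3.5 uses it in judging whether the work affected measured experience. A reader who believes that 11 points was reliably detectable could take a non-significant ward result as evidence that nothing improved, when power for a change of that size may have been well below 80%.

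**Working it through.** **Inputs from the protocol.** Mailed per ward and wave: 240 (section 5.2). Response: 50%, so n = 240 × 0.5 = 120 per wave. Two independent groups of equal size (section 3.4).

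**Inputs not in the protocol, assumed here.** Two-sided 5% (z = 1.96), 80% power (z = 0.8416), baselines from 50% to 85%, upward change.

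**Can 11 be reproduced?** Not from the stated inputs, since four of the quantities needed are missing. It can be matched in several ways:

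- 95% margin of error of a difference with both proportions at 0.75: 1.96 × √(2 × 0.75 × 0.25 / 120) = 10.96 points. This makes no allowance for power.
- One-sided 5%, 80% power, rise from 80%: 11.2 points.
- Finite population correction for a census with half responding (variance × 0.5), 80% power, rise from 70%: 10.97 points. Treating all 240 mailed patients as responders gives the same number.
- A 0-100 mean score with SD 30: 2.8016 × 30 × √(2/120) = 10.8 points. Section 5.2 speaks of percentage points and gives no SD.

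Nothing in the protocol shows which of these, if any, was used.

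**Formula.** With d = p2 − p1 and p̄ = (p1 + p2)/2, using the pooled normal approximation:

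power = Φ{ [d√n − 1.96 √(2p̄(1 − p̄))] / √(p1(1 − p1) + p2(1 − p2)) }

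**Power for an 11-point rise from 50%.** p1 = 0.50, p2 = 0.61, p̄ = 0.555.

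- d√n = 0.11 × 10.954 = 1.205
- 1.96 × √(2 × 0.555 × 0.445) = 1.96 × 0.7028 = 1.378
- Denominator: √(0.2500 + 0.2379) = 0.6985
- Power = Φ(−0.247) = 0.40

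**Power for an 11-point rise from 84%.** p1 = 0.84, p2 = 0.95, p̄ = 0.895.

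- 1.96 × √(2 × 0.895 × 0.105) = 0.850
- Denominator: √(0.1344 + 0.0475) = 0.4265
- Power = Φ[(1.205 − 0.850)/0.4265] = Φ(0.833) = 0.80

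**Minimum detectable rise from 50%.** Try d = 0.1771, so p2 = 0.6771 and p̄ = 0.5886.

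- d√n = 1.940
- Required: 1.96 × √(2 × 0.5886 × 0.4114) + 0.8416 × √(0.2500 + 0.2186) = 1.364 + 0.576 = 1.940

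The two sides agree, so the figure is 17.7 points.

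**Across baselines (n = 120 per wave, two-sided 5%):**

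| Baseline | Minimum detectable rise, 80% power (points) | Power for an 11-point rise |
|---|---|---|
| 50% | 17.7 | 40% |
| 54% | 17.4 | 41% |
| 60% | 16.7 | 43% |
| 70% | 15.0 | 51% |
| 75% | 13.9 | 58% |
| 80% | 12.4 | 68% |
| 84% | 11.0 | 80% |
| 85% | 10.6 | 83% |

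At the 49% response of the reference survey (117.6 responses), the first two rises become 17.9 and 17.6 points.

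**Significance threshold alone.** With both proportions at 0.5, 1.96 × √(2 × 0.25 / 120) = 12.65 points. Near 50%, an observed 11-point difference would not reach two-sided p < 0.05 without a finite population correction.

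**Responses per wave for 80% power at 11 points.** 320 from 50%, 312 from 54% (312/120 = 2.6 times the plan), 239 from 70%, 160 from 80%.

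**The case against.** The strongest reply is that the protocol states no power, alpha or baseline, so there is no calculation to contradict, and 11 points is attainable. It holds at 80% power from about 84% upward, and lower down under one-sided testing or a finite population correction. This stands as far as it goes: a reader might infer that the 11 is an arithmetic error, and the document does not show that. It does not rescue the figure as a general ward statement. From a 50% baseline, one-sided 5% testing gives 53% power for 11 points and the finite population correction gives 68%. The protocol mentions neither.

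A reader might also take 17-18 points as the study's true detectable difference because 54% and 50% appear in section 1. Those are national background results, not design inputs. The outcome is still open, and three of the six Trusts are to be chosen as high performers, so ward baselines may be higher.

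Nor does the protocol support a claim that most real 11-point gains would be missed. That holds only below a baseline of about 70%.

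Finally, the protocol already plays down the survey: small changes are out of reach, it is one source among several, and reports will carry cautions. This limits the consequence and the severity. It does not correct the number. A warning about small changes, placed beside an 11-point figure, suggests that 11 points itself is safely detectable.

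**Conclusion.** The point holds in a limited form. The unconditional 11-point figure is wrong as a general statement of what 120 responses per wave can detect. At two-sided 5% and 80% power it applies only to rises from a baseline of about 84% or more, and the table above shows how far it falls short below that.

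This rests on two independent samples of 120, a normal approximation without finite population correction, and the conventional error rates, which are assumptions because the protocol gives none. How much it matters in any ward depends on the outcome chosen and its baseline, both unknown. Severity is moderate: the study is exploratory, ward throughput limits the sample, and no conclusion rests on the survey alone.

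**What to change.** In section 5.2, replace the single figure with a range by baseline, for example:

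> With 120 responses per wave, a two-sided 5% comparison has 80% power for a rise of about 17-18 points from a baseline of 50-54%, 15 points from 70% and 12 points from 80%.

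If 11 was meant as a 95% margin of error, or rests on other assumptions, say so and give them. Carry the restated figure into the report cautions already promised in sections 3.1 and 3.4, so that a non-significant ward result is not read as no impact.

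The cost is a sentence or two in section 5.2 and matching wording in the reports. No extra patients or longer sampling period are needed. The one drawback is that the stated sensitivity of the survey becomes less favourable.

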### Baseline and follow-up interviews about patient experience

Size of sample: 8 per ward at baseline, and a further 8 per ward at post-intervention follow-up. Total 96 across six wards.

Sampling technique: Purposive sample selected from survey respondents (see previous section), to add qualitative insight to survey responses. Variation will be sought across survey patient experience scores, to include a range of positive, negative and mixed experiences. It is anticipated that the sample will also include some responses from family members/ carers who have completed the survey on behalf of a person who lacks capacity. Responses will be treated the same as patient responses.

Recruitment/sample identification: Survey respondents (see above) will be invited to express interest in taking part in an interview, either face-to-face or by telephone according to their preference. A subset of those volunteering (including family members/carers) will be selected according to scores (see above) and will be sent a participant information sheet in the post.

Consent: Potential participants will be given a week to read the participant information sheet. They will then be contacted by a member of the research team to discuss the study and answer any queries, and to arrange a date for interview. This telephone call will also offer an opportunity for the researcher to assess the person's capacity. Those preferring a telephone interview will be sent a consent form and reply-paid envelope in the post; those preferring a face-to-face interview will sign consent on the day of the interview.

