## 7.8 Data protection and confidentiality

All information will be handled in confidence in accordance with the UK Data Protection Act 1998. The Principal Investigator will be responsible for security and access to the data. At the end of the study the research data will be secured for five years in keeping with standard research practice and then destroyed. Any personal identifiers relating to individual participants will be held for less than three months after the end of this 27-month study.

Individual survey respondent data will be held securely, confidentially and anonymously by the Picker Institute and will not be shared with other co-investigators. The Picker Institute has United Kingdom Accreditation Service

Understanding how frontline staff use patient experience data for service improvement - an exploratory case study evaluation.

Protocol V1 09.02.16 HRA 180418

(UKAS) accredited certification for its information security management system (ISO27001:2013). Survey respondents who are interested in taking part in an interview will be invited to register their interest on the survey. In this case, the research team will send the unique survey ID codes of those selected for interview to the Trust and ask for a list of names and addresses to be supplied. It will be explained to all participants that if they tick the box registering interest in being interviewed, they will be agreeing for the hospital to pass on their name and address so that the research team can send them more information, but that all answers they provide on the survey will remain entirely anonymous and will not be individually identifiable.

Any recordings, handwritten or typed fieldnotes made during interviews or observation will be stored confidentially on password protected computers. Transcripts of interviews will be anonymised and given a unique ID number. The digital recording and the transcript, identified only by the code number, will be kept in a secure place at the Nuffield Department of Primary Care Health Sciences, University of Oxford (case study interviews), or the Nuffield Department of Population Health, University of Oxford and the Picker Institute (baseline and follow up patient experience interviews). Information linking the names of respondents to ID numbers will be kept separately in hard copy in a locked filing cabinet in the same locations. Quotations used will not be personally identifiable.

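### The survey promises full anonymity, but responses are coded, and interviewees are chosen on their scores and then traced to names through their survey IDs

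*Protocol*

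**What the plan says.** Protocol 5.2, patient survey, Consent, describes what all participants will be told, including those who tick the box to be considered for interview: "all answers they provide on the survey will remain entirely anonymous and will not be individually identifiable". Section 7.8 repeats the statement. Under 5.2, returning the questionnaire counts as consent.

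The recruitment text in the same subsection has the Trust do the mailing and the replies go to the Picker Institute (the survey organisation). For those wanted for interview, the team will "send the unique survey ID codes of those selected for interview to the Trust and ask for a list of names and addresses". Section 7.8 gives the same route.

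The interview subsection of 5.2 gives the basis for selection: "Variation will be sought across survey patient experience scores, to include a range of positive, negative and mixed experiences". Volunteers "will be selected according to scores (see above) and will be sent a participant information sheet in the post".

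There are safeguards. Section 7.8 keeps individual survey data at the Picker Institute and away from the other co-investigators. Section 7.12 passes only aggregated findings to the rest of the team and to the Trust. Volunteers are told that the hospital will release their name and address.

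**The concern.** Data are anonymous when nobody can get from a set of answers back to a person. Here a route back exists by design, and the plan uses it for exactly the people to whom the promise is addressed: those who tick the interview box. They are told that their contact details will be released. Nothing in the protocol says they will be told that their answers decide whether they are approached, or that those answers can be linked to their name.

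What is at stake is consent and disclosure, not an estimate. In a survey that the protocol itself rates as minimal risk, disclosure of what someone said about their care is the main risk a participant runs. The statement about who can trace the answers should therefore be accurate.

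**Working it through.** No statistical figure underlies this point. The check is a comparison of the passages, followed by a count.

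**Comparison**

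1. *The promise.* 5.2 (survey, Consent) and 7.8: answers are anonymous and not identifiable to an individual. No limit is attached, such as anonymity towards the hospital only or in reports only.
2. *The code.* 5.2 (survey, Recruitment) and 7.8: each survey has a unique ID, and the Trust can convert it to a name and address. Every returned questionnaire is therefore coded.
3. *Use of individual answers.* 5.2 (interviews): selection aims for a spread of positive, negative and mixed scores. Whoever selects must read each volunteer's scores against that volunteer's ID.
4. *Resolving the code.* 5.2 and 7.8: "the research team will send the unique survey ID codes of those selected for interview to the Trust", and names and addresses are requested in return.

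Steps 3 and 4 form a chain from score to ID to name. Both ends lie within the research team, because the team makes the selection and receives the names. That contradicts step 1 for the people selected. For everyone else who replies, the answers are still coded, but the documents describe nobody holding both the name and the answers.

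The reminder procedure fits this picture, with "2 reminder mailings being sent to non-responders during this period". Mailing only non-responders implies that return status can be traced by person or by ID. This is an inference, since the mechanics are not described, and return status reveals no answers. It supports the view that the survey is coded and shows nothing more.

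**Count** (inputs from 5.2)

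- Questionnaires sent: 6 wards × 240 × 2 waves = 2,880, the protocol's own total.
- Expected returns at a 50% response: 2,880 × 0.50 = 1,440.
- Planned interviewees: 6 wards × 8 × 2 waves = 96, the protocol's own total.
- Share of expected returns selected and linked to a name: 96 / 1,440 = 6.7%. Anyone selected who then declines adds to this, because the name is obtained before the invitation is posted.

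**The case against.** The case on the other side is substantial, and much of it stands.

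- *The hospital does not see answers.* This stands. Replies bypass the Trust, and it receives aggregated findings only. A reader might infer that the hospital can find out what its patients said. The documents do not support that: the Trust learns who was selected, and because positive, negative and mixed scorers are all chosen, selection alone does not mark anyone as a critic.
- *Direct linkage affects few people.* This stands. It concerns those selected, all of them volunteers who were told that their contact details would be released.
- *Score-based sampling does not itself need a name.* This stands. A reader might infer that the purposive sample and any protection of identity are incompatible. They are not: selection can run on codes, with names and answers kept apart. The protocol does not say that the returned list is matched to IDs, or that interviewers see scores. It also does not rule out either, and the team that sent the IDs can make the link.
- *The ID numbers in 7.12 may be interview transcript numbers.* They may be, and the point does not rest on that section.
- *Biased answers.* A reader might infer that the arrangement makes patients reluctant to criticise. The documents give no support for this. A strong promise of anonymity would, if anything, encourage candour, and 3.1 already accepts that interviewees are not representative.
- *The survey materials are not shown.* This is true. The protocol only reports what will be explained, and the materials go to ethics review. But the protocol sets what they are to say, and it says it twice.
- *The sentence may mean anonymity towards the hospital or in publications.* That is plausible, but the text carries no such limit. The repair is to write the limit in.

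None of this makes the unqualified promise true for people whose scores are read, whose IDs are resolved and whose names are returned.

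**Conclusion.** The point holds as a contradiction between a statement to participants and the procedure the protocol describes. The survey is confidential and coded, not anonymous. Linkage of answers to a name within the research team arises for about 96 people, 6.7% of some 1,440 expected returns, plus any selected who decline. The inaccurate statement is intended for all 2,880 people mailed.

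This rests on two assumptions: that the survey materials follow the protocol's description, and that the 50% response and 8 interviews per ward per wave are achieved. The contradiction itself depends on neither figure. The sample size and the comparison of the two surveys are unaffected.

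**What to change.** Before the baseline mailing:

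1. In 5.2 (survey, Consent), 7.8 and the survey materials, replace the anonymity promise. Say that answers are confidential, held under a code by the survey organisation, and not shown individually to the hospital.
2. In the same places, tell those who volunteer for interview that their answers will be used to choose interviewees and can be linked to their name for that purpose.
3. In 7.8 and 7.12, state that the survey organisation makes the score-based selection, and name by role who holds the link between survey ID and name.

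The recruitment route can stay as it is. Having volunteers send contact details straight to the survey organisation would give the holder of the answers the names of all volunteers, not only those selected, so it is not recommended here.

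The cost is a wording change in the protocol and survey materials, and a slightly less reassuring statement to respondents.
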